The purpose of this pilot project is to gather feasibility data to support grant development for a combined alcohol and smoking tele-health mCM intervention that will effectively treat both disorders. The study will be undertaken with the following objectives:

- 1) Develop a multi-component alcohol and smoking tele-health mCM intervention in two successive cohorts of five participants. The first cohort of treatment completers (n = 5) will provide qualitative data from participants and therapists, which will be utilized to modify the treatment components including the therapist manual, mCM apps, and data collection procedures. The second cohort (n = 5) will yield qualitative and quantitative data to refine the intervention and in preparation for a pilot trial.
- 2) Evaluate the feasibility and acceptability (e.g., mCM app reliability, mCM app procedures completion, patient satisfaction) of a tele-health mCM intervention; relative to a comparison group receiving a tele-health intervention without mCM, This will be evaluated in a third cohort that will include a pilot trial randomizing participants to telehealth with mCM (n = 30) or to a comparison group receiving the same phone counseling (Cognitive Behavioral Therapy; CBT) and tele-medicine without mCM (n = 15).

Methods:

Study Design

A successive cohort design will be used to refine the intervention, resulting in three cohorts of participants with AUD and cigarette use. The first two cohorts will focus on treatment refinement, followed by a third cohort participating in a pilot trial.

Successive Cohort Design Stage 1: Feasibility

The successive cohort design (SCD; Epstein et al., 2007) is an iterative process designed to systematically refine and modify behavioral treatments in the early stage of development. The SCD model is a good fit for Stage 1 research, which is designed to generate or modify existing protocols and conduct preliminary testing before initiating larger efficacy trials (Stage II) and effectiveness research (Stage III).

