The first cohort of five participants will complete the tele-health mCM intervention and provide evaluative feedback during an in-depth interview administered at the end of the study, and described in the Measures section below. A coding scheme will be developed for categorizing comments made during the interview based on the study components (e.g., mCM procedures, CBT, interface with smart phone app), subcomponents (e.g., mCM feasibility, CBT burden), and the evaluations drawn (e.g., CBT session too long, video upload still unclear after mCM training).

Successive Cohort Design Stage 2: Treatment Refinement

After the intervention and study have been modified based on information learned from the first cohort, we will treat a second cohort ($n = 5$). Though qualitative data will be evaluated and utilized using methods similar to those of the first cohort, the second cohort will more closely evaluate quantitative data. We will explore relationships of sociodemographic, baseline substance use, and psychiatric comorbidity variables with treatment retention and outcomes. This will identify treatment components to modify or enhance to maximize treatment effectiveness.

Successive Cohort Design Stage 3: Pilot Trial

After treatment modifications from cohort 2, we will conduct a pilot randomized controlled clinical trial. The primary goal of the trial is to evaluate the efficacy of a combined tele-health mCM intervention. The pilot trial will use a two-group design in which 45 participants with an AUD who smoke regularly will be randomized to either:

TELE-HEALTH MOBILE CONTINGENCY MANAGEMENT (mCM) INTERVENTION, a proactive tele-health intervention that combines evidence-based telephone CBT for alcohol and smoking cessation, a tele-medicine clinic for access to nicotine replacement therapy (NRT), and intensive CM therapy administered *via* a smart-phone based application (CM).

OR

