TELE-HEALTH FOR ALCOHOL AND SMOKING CESSATION, a proactive tele-health intervention that will provide controls for therapist, medication, time and attention effects. The tele-health intervention provides the same evidence-based telephone CBT for alcohol and smoking cessation, and tele-medicine clinic for access to smoking cessation pharmacotherapy as in the mCM intervention, but does not include mCM. Instead, participants will receive monetary compensation for each assessment, regardless of abstinence (\$3.00 for breathalyzer, \$1.00 for CO). No escalating or reset contingencies will be used to alter monetary compensation amounts in this group. Mobile assessments of abstinence will occur on the same schedule as the tele-health mCM condition.

C.9.2. Participant Recruitment, Eligibility, and Screening

A total of 55 participants with AUD and smoking will be enrolled across the three cohorts. Participants will be recruited from primary care and substance abuse clinics at

Duke University. We will also post flyers at local hospitals and in community settings. To allow more detailed analysis of the tele-health mCM intervention that is the focus of this study, the pilot trial conducted with the third cohort will randomize 30 participants to the tele-health mCM intervention, and 15 to the tele-health smoking cessation comparison condition.

Completers of the proposed tele-health mCM intervention will provide self-report data and evaluative feedback during an in-depth interview administered at the end of treatment, and described in the Assessments section below. Content analysis of the resulting data will evaluate study components (i.e., mCM procedures, CBT, interface with smart phone app, NRT utility and adherence) and subcomponents (e.g., mCM feasibility, CBT burden) that they address and the evaluations drawn (e.g., CBT session too long, video upload still unclear after mCM training). We will explore sociodemographic, substance use, and psychiatric comorbidity variables to examine the magnitudes of their associations with treatment retention and outcomes. This will identify areas of the treatment potentially in need of modification or enhancement to maximize its effectiveness. A summary of the findings will be evaluated by our team of clinical researchers (Drs. [name], [name], [name]), all of whom are experienced in treatment development and trial design, will evaluate a summary of the findings and determine changes to make to the intervention.

Recruitment

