We will additionally explore differences in alcohol and smoking abstinence outcomes by treatment. Because the tele-health only intervention is expected to have a uniformly small impact on alcohol and smoking outcomes in comparison to the tele-health mCM intervention, implementation of an imbalanced-samples design, with twice as many participants randomized to the tele-health mCM treatment as to the tele-health only treatment, should maximize power for identifying treatment effects. That said, the proposed sample has 80% power to detect a treatment effect equivalent to Cohen's $d = 0.76$. For reference, in our pilot study of 22 smokers with PTSD, tele-health mCM yielded an effect size of Cohen's $d = 0.79$ at the 3-month follow-up. In particular, comparisons by treatment at post-intervention, 6 week follow-up, and 6-month follow-up will be made regarding alcohol consumption (drinks/week, number of heavy drinking episodes, proportion of days abstinent, and achieving recommended drinking limits) and smoking (number of cigarettes smoked each day and number of days of smoking abstinence) *via*

generalized linear modeling, which can accommodate normally and non-normally distributed (e.g., count) variables.

References

- Acuff, S. F., & Murphy, J. G. (2017). Further examination of the temporal stability of alcohol demand. *Behavioural Processes, 141*, 33-41. doi:10.1016/j.beproc.2017.03.020.
- Alessi, S. M., & Petry, N. M. (2013). A randomized study of cellphone technology to reinforce alcohol abstinence in the natural environment. *Addiction, 108*(5), 900-909. doi:10.1111/add.12093
- drinking outcomes in clinical trials. *Journal of Studies on Alcohol, 61*, 55-63.
- Bechara. A., Damasio, A.R., Damasio, H., Anderson, S.W. (1994). Insensitivity to future consequences following damage to human prefrontal cortex. *Cognition, 50*, 7-15.

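### The stated 80% power at d = 0.76 does not follow from 30 versus 15: conventional 5% t-tests give about 65% (two-sided) or 76% (one-sided), and no stated input closes the gap

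*Combined protocol and SAP*

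**What the plan says.** The Objectives section describes the third cohort as "randomizing participants to telehealth with mCM (n = 30) or to a comparison group receiving the same phone counseling" and tele-medicine without mCM (n = 15). Section C.9.2 repeats the split: the trial "will randomize 30 participants to the tele-health mCM intervention, and 15 to the tele-health smoking cessation comparison condition". That section's reason for the 2:1 ratio is to allow "more detailed analysis of the tele-health mCM intervention that is the focus of this study".

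In Data Analyses, under Specific Aim 2, a second reason appears. The tele-health only arm "is expected to have a uniformly small impact on alcohol and smoking outcomes", so an imbalanced design "should maximize power for identifying treatment effects". The power claim follows: "the proposed sample has 80% power to detect a treatment effect equivalent to Cohen's" d = 0.76. For reference, the plan then cites d = 0.79 at 3 months from the sponsor's pilot in 22 smokers with PTSD.

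The same paragraph says that "comparisons by treatment at post-intervention, 6 week follow-up, and 6-month follow-up will be made regarding alcohol consumption" and smoking, by generalized linear modeling. The start of Data Analyses says that the correlation structure of the longitudinal variables will be explored, but gives no value for it.

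**The concern.** A power figure can be used only if a reader can rebuild it from the sample size, error rate, test and effect. Here only the sample size and the effect are given, and the usual choices for the rest do not lead to 80%.

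Placing 0.76 just below the pilot's 0.79 invites the inference that an effect like the pilot's would very probably be found. If real power is well below 80%, a null result is weaker evidence against the intervention than it will appear. Feasibility is the stated purpose in the Objectives section, but the Stage 3 section says "The primary goal of the trial is to evaluate the efficacy of a combined tele-health mCM intervention", and Data Analyses says that information on effects will feed the planning of a full RCT. An over-read null result could therefore count against that trial.

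The claim that 2:1 allocation maximizes power has the same gap. It holds only under a ratio of SDs that the plan does not state.

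**Working it through.** **Inputs from the plan.** n = 30 and 15 (Objectives; C.9.2). d = 0.76, power 80%, reference d = 0.79 (Data Analyses, Specific Aim 2).

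**Inputs assumed because the plan is silent.** Alpha 5%, one- and two-sided; two-sample t-test; equal SDs; no covariate; no attrition, which favours the plan.

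**Attempt to reproduce the 80%.**

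- Standard error of the difference in SD units: sqrt(1/30 + 1/15) = sqrt(0.100) = 0.316.
- Noncentrality at d = 0.76: 0.76 / 0.316 = 2.40. At d = 0.79: 0.79 / 0.316 = 2.50.
- Degrees of freedom: 30 + 15 − 2 = 43. Critical t: 2.017 two-sided, 1.681 one-sided.
- Power is the probability that a noncentral t variable with 43 df and that noncentrality falls beyond the critical value.

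| Test at 5% | Power at 0.76 | Power at 0.79 | d detectable with 80% power |
|---|---|---|---|
| Two-sided | 65.2% | 68.5% | 0.906 |
| One-sided | 76.4% | 79.2% | 0.799 |

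A simulation of 200,000 trials at d = 0.76 gave 65.2% and 76.5%. The normal approximation gives 67.1% and 77.6%, so the most favourable conventional variant still misses by 2.4 points. The shortfall with the t-test is 80 − 65.2 = 14.8 points two-sided, or 80 − 76.4 = 3.6 points one-sided.

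**What would be needed to reach 80% at 0.76 with 30 versus 15.** Each row changes one input only.

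| Change | Two-sided | One-sided |
|---|---|---|
| Larger alpha | 12.6% | 6.3% |
| One baseline covariate: divide d by sqrt(1 − r²) | r about 0.55 | r about 0.31 |
| Mean of three assessments: divide d by sqrt((1 + 2ρ)/3) | ρ about 0.55 or lower | ρ about 0.86 or lower |
| mCM SD larger than control SD (Welch test, d on pooled SD) | ratio about 1.8 | ratio about 1.2 |

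Here ρ is the within-person correlation between assessments. If d is instead put on the average SD, the two-sided detectable effect is still 0.811 at an SD ratio of 2; one-sided, a ratio of about 1.4 gives 0.756. None of these values is in the plan. The averaging route also departs from the plan's wording, which describes comparisons at each time point.

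**Other sample sizes that come close.** At d = 0.76, 45 split equally gives 80.6% one-sided; 40 versus 15 (counting the ten non-randomised participants of cohorts 1 and 2 as mCM) gives 79.8% one-sided; 55 split equally gives 79.0% two-sided. These may hint at where the figure came from, but none is the randomised comparison.

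**Allocation.** With equal SDs, 22 versus 23 gives 70.2% two-sided, against 65.2% for 30 versus 15. With an mCM-to-control SD ratio R, the variances of the two designs are equal when R²/30 + 1/15 = R²/22.5 + 1/22.5, so R² = 2 and R = 1.41 (1.45 by the Welch test). The best split of 45 is 22/23 at R = 1, 27/18 at R = 1.5 and 30/15 at R = 2.

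**The case against.** The strongest reply is that this is under-specification, not proven arithmetic error. The plan never says that the figure comes from an unadjusted t-test. It names generalized linear modeling, and a covariate, repeated assessments or unequal SDs could give 0.76. If the sponsor meant a one-sided test, modest inputs are enough: r of about 0.31, or an SD ratio of about 1.2 on the pooled SD. The expectation of a uniformly small response in controls is a qualitative reason to think that their spread is smaller, which would also favour 2:1. The abstinence comparison is introduced as exploratory, the aim is feasibility, and no decision is tied to a p-value.

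Much of this stands. The 80% is not impossible, and the 15-point gap is the unfavourable end of a range of roughly 4 to 15 points. The allocation point is secondary, since C.9.2 gives an independent and sound reason for 2:1. But every rescue needs at least one value that the plan does not state, and the easier ones also need an unstated one-sided test. Naming a model family is not a power assumption. The exploratory framing limits the consequence, but it sits beside a sentence that makes efficacy the trial's primary goal.

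**Conclusion.** The concern holds: the power sentence is wrong as written. For the 30 versus 15 that the plan fixes, conventional 5% t-tests deliver 65% (two-sided) or 76% (one-sided) at d = 0.76. An effect of the pilot's size would be missed about 31% or 21% of the time.

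These figures assume an unadjusted comparison, equal SDs and complete data. Attrition lowers them: if, for illustration, about 70% were analysed (21 versus 10), two-sided power at 0.76 would be about 48%. The maximize-power claim for 2:1 is likewise unsupported without an SD ratio above about 1.4, and 2:1 is the best split only near 2.

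The d figure also does not describe the primary end-point in Outcome Measurement and Biochemical Verification, which is prolonged abstinence, a yes/no outcome. This should be fixed, but the feasibility purpose keeps it from being more serious.

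**What to change.** Either of two changes to the power sentence is enough.

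1. If 0.76 came from a specific calculation, state its alpha, sidedness, test, outcome and time point, together with the covariate correlation, averaging rule or SD ratio used.
2. Otherwise replace it with: *With 30 versus 15 randomised, an unadjusted two-sided 5% t-test has 80% power for d of about 0.91, and about 65% power for d = 0.76 (about 69% for the pilot's d = 0.79), before attrition.*

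Two smaller edits are worth making at the same time. For the 2:1 ratio, rely on the reason in C.9.2 or state the SD ratio assumed. Add a sentence saying that the d figure does not apply to prolonged abstinence.

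The cost is wording only, with no change to the sample size or design. The stated power becomes less favourable, or the assumption behind it becomes visible.

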Self-reported and bioverified prolonged abstinence from alcohol, smoking, and dual abstinence at the 6-month follow-up will be the primary end-point. Prolonged abstinence will exclude substance use in the first two weeks following the quit date to give participants time to achieve initial abstinence (Hughes et al., 2003). Self-reported prolonged abstinence will be verified by breathalyzer alcohol assessment and assay of cotinine, a metabolite of nicotine in the saliva. Saliva samples will be collected from participants at end of treatment, and at 6-month follow-ups. Deidentified saliva samples will be sent to Salimetrics, and there they will be analyzed for the presence of cotinine using a standard cut point of 10 ng/ml to determine abstinence. A blind sample of 5% will be run again to assure test accuracy of saliva samples. All participants will be asked to provide saliva samples. However if it seems likely that they will have a positive saliva cotinine according to the Tobacco Exposure Questionnaire administered at end of

monitoring at 6-month follow-up, the collected sample may not be sent to Salimetrics for testing.

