Participants will also report alcohol consumption patterns such as standard drinks/week, heavy drinking episodes (drinking enough so that BrAC would have reached 0.08g/dL), proportion of days abstinent, and achieving recommended drinking limits (≤ 14 drinks/wk and < 5 drinks/day for men; ≤ 7 drinks/wk and < 4 drinks/day for women). Because bioverification of long-term alcohol abstinence is not substantially more reliable than self-report (Babor, Steinberg, Anton, & Del Boca, 2000), alcohol outcomes will primarily be assessed with self-report. Participants will provide breathalyzer verification of alcohol abstinence at the end of Thinning mCM and 6-month follow-up visits. Participants will also report number of cigarettes smoked each day, and days of smoking abstinence. Collection of alcohol and smoking use data will allow for calculation of dual abstinence days and longest duration of dual abstinence. Participants will be asked to submit a saliva sample for biochemical validation. Saliva will be stored in a freezer in a locked office. At the end of the study, the project coordinator will personally mail all saliva samples to the appropriate laboratory to be analyzed for the presence of cotinine. The saliva will only be tested for cotinine, a by-product of nicotine. This method yields response rates that are comparable to in-person collection methods (i.e., 70%). A standard cut-point of 10 ng/ml will be used to discriminate those who are abstaining from those who are continuing smokers.

Prolonged abstinence from alcohol will be assessed using phosphatidylethanol (PEth) as a biomarker at the 6-month follow-up visit. While self-report abstinence has been a proven indicator, bioverification using PEth testing is an effective tool for identifying heavy drinking (Nanau & Neuman, 2015), and has a 99% sensitivity for detecting excessive alcohol consumption (Aradottir et al., 2006). This will be assessed using a dried blood spot collection, collecting 3 spots (about 3 mL) of blood from the participants' finger. PEth testing has been shown to have. The de-identified test card will be collected by ARCpoint labs of Raleigh Durham for analysis. All sharps and biohazardous material will be collected and disposed of by ARCPoint labs.

Data Analyses

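### The only power statement (80% at Cohen's d = 0.76) is on a two-means scale, gives no basis for the yes/no primary end-point at 30 v 15, and does not reproduce at 30 v 15 for means either

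*Combined protocol and SAP*

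**What the plan says.** Outcome Measurement and Biochemical Verification sets the primary end-point: "Self-reported and bioverified prolonged abstinence from alcohol, smoking, and dual abstinence at the 6-month follow-up will be the primary end-point". For smoking, the same section makes the classification explicitly two-way: "A standard cut-point of 10 ng/ml will be used to discriminate those who are abstaining from those who are continuing smokers". The randomized comparison is in the third cohort, which "will randomize 30 participants to the tele-health mCM intervention, and 15 to the tele-health smoking cessation comparison condition". On that trial, the Stage 3: Pilot Trial section says: "The primary goal of the trial is to evaluate the efficacy of a combined tele-health mCM intervention".

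Under Data Analyses, the Specific Aim 2 paragraph on outcomes opens: "We will additionally explore differences in alcohol and smoking abstinence outcomes by treatment". It then gives the plan's one power figure: "the proposed sample has 80% power to detect a treatment effect equivalent to Cohen's $d = 0.76". For context it adds that, in an earlier pilot of 22 smokers with PTSD, "tele-health mCM yielded an effect size of Cohen's $d = 0.79$ at the 3-month follow-up". The outcomes it goes on to list are amounts, counts and proportions of days, plus one yes/no item (keeping within recommended drinking limits). Prolonged abstinence is not in that list. The power statement names no outcome, alpha, sidedness, abstinence rate or allowance for dropout.

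**The concern.** The plan has a binary primary end-point and a power figure on a scale made for means. Because the paragraph opens on abstinence, a reader will naturally take 80% as the chance of detecting an mCM effect on abstinence. Nothing in the plan supports that, and a correct d for the drinking and smoking quantities would still not describe the power of the abstinence comparison.

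What is at stake is interpretation. Data Analyses says the pilot should inform a full RCT, including by giving information on effects. A non-significant abstinence result set beside a claimed 80% could be taken as evidence against mCM when the design had much less power than that.

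**Working it through.** **Inputs from the plan.** 30 mCM and 15 comparison participants; d = 0.76; stated power 80%; 55 enrolled over three cohorts (5 + 5 + 45).

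**Assumptions, because the plan is silent.** Alpha 5%, two-sided unless stated; comparison-arm abstinence of 10%, 20% or 30%; everyone assessed; one abstinence component tested, with no multiplicity adjustment.

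**Step 1: the plan's own figure, as a two-sample t-test.** The noncentrality is d / √(1/n₁ + 1/n₂) = 0.76 / √(1/30 + 1/15) = 0.76 / 0.3162 = 2.40, on 43 degrees of freedom.
- Two-sided (critical t 2.017): power 65%.
- One-sided (critical t 1.681): power 76%.
- 80% power two-sided needs d of about 0.91.

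The stated 80% is approached only for samples other than the planned comparison: 27 v 28 two-sided (79.0%), 22 v 23 one-sided (80.6%) and 40 v 15 one-sided (79.8%). All three are tests of means.

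**Step 2: turn d = 0.76 into two proportions.** There is no unique conversion, so three were used, with p₀ the comparison-arm rate.
- Logistic: OR = exp(0.76 × π/√3) = exp(1.378) = 3.97, and p₁ = OR·o/(1 + OR·o) with o = p₀/(1 − p₀). At p₀ = 10%, 3.97 × 0.111 = 0.441, and 0.441/1.441 = 30.6%.
- Probit: p₁ = Φ(Φ⁻¹(p₀) + 0.76).
- Cohen's h = 0.76: p₁ = sin²(arcsin√p₀ + 0.38).

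**Step 3: exact power.** Sum the binomial probabilities b(x; 15, p₀) × b(y; 30, p₁) over those of the 16 × 31 possible tables in which the test rejects.

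| Conversion | p₀ | p₁ | Fisher, two-sided | Uncorrected chi-square, two-sided | Uncorrected chi-square, one-sided |
|---|---|---|---|---|---|
| Logistic | 10% | 30.6% | 26.7% | 35.4% | 45.9% |
| Logistic | 20% | 49.8% | 41.4% | 49.5% | 64.7% |
| Logistic | 30% | 63.0% | 47.1% | 55.0% | 71.0% |
| Probit | 10% | 30.1% | 25.4% | 34.0% | 44.5% |
| Probit | 20% | 46.7% | 34.3% | 42.0% | 56.5% |
| Probit | 30% | 59.3% | 37.2% | 45.1% | 62.1% |
| Cohen's h | 10% | 41.7% | 56.8% | 65.2% | 74.8% |
| Cohen's h | 20% | 55.8% | 56.3% | 64.5% | 78.7% |
| Cohen's h | 30% | 67.1% | 58.9% | 66.0% | 79.7% |

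At a lower comparison-arm rate of 5%, the logistic conversion gives p₁ = 17.3% and Fisher power of about 7%.

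**Step 4: how much of the gap is due to the end-point type.** At 30 v 15 the power for means is 65%, so the first 15 points below 80% (80 − 65) arise before the end-point type matters. Under the logistic conversion, the further loss from 65% is 65 − 47 = 18 to 65 − 27 = 38 points with Fisher, or 65 − 55 = 10 to 65 − 35 = 30 points with chi-square. With Cohen's h and two-sided chi-square there is essentially no further loss.

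**Step 5: what 30 v 15 can detect.** For 80% power (Fisher, two-sided 5%), mCM abstinence must be about 52% against 10%, 66% against 20%, or 75% against 30%. These are odds ratios of about 9.7, 7.7 and 7.0.

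**The case against.** The best defence is context. The Objectives section describes a feasibility project to support a grant application, Aim 2 concerns feasibility and acceptability, and the outcome comparisons are introduced as additional exploration. The measures listed after the power sentence are nearly all quantities, two of them counting or averaging days of abstinence, so a d-scale statement suits that list and need not have been meant for prolonged abstinence. The sentence also speaks of an effect equivalent to d, not of d itself. All of this stands, and it limits the seriousness of the point. It does not remove it: the plan elsewhere calls abstinence primary and efficacy the trial's main goal, and no two-sided conversion tried makes the equivalence hold at 80%.

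A reader might infer three stronger things that the documents do not support.
- That the 80% is right for means and was only applied to the wrong outcome. It is not right for means at 30 v 15, so the whole gap cannot be blamed on the binary end-point.
- That power for abstinence is a single known figure. It depends on an assumed rate, alpha, test and conversion, none of which the plan states.
- That the trial would more often miss this effect than find it. That holds for Fisher's test under the logistic and probit conversions at 10-30%. It fails for Cohen's h, and for one-sided chi-square under the logistic conversion at 20% and 30%.

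Nor does any section make the full RCT depend on a significant abstinence result. The risk of misreading is plausible but is not written into the plan.

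**Conclusion.** The point holds in a limited form. The plan gives no power basis for its primary end-point, and its one power figure does not carry over to it. At 30 v 15 and two-sided 5%, with comparison-arm rates of 10-30%, an effect matched to d = 0.76 by the logistic rule has 27-47% power (Fisher) or 35-55% (uncorrected chi-square). The probit rule is lower, at 25-37% with Fisher. Cohen's h is higher, at 56-59% or 65-66%. Only Cohen's h with a one-sided uncorrected chi-square approaches 80% (75-80%). The figure also fails on its own scale at the planned allocation, with 65% two-sided or 76% one-sided. The rates, alpha, sidedness and conversion are assumptions; the mismatch of scale and the lack of any figure for abstinence are not. This should be corrected, but it does not undermine the pilot's feasibility aims.

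**What to change.** Change the Specific Aim 2 text under Data Analyses as follows.

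- Restate the d figure for the continuous drinking and smoking outcomes at the planned allocation: 30 v 15 gives 80% power, two-sided 5%, at d of about 0.91. Limiting the present sentence to those outcomes without changing the number would leave a claim that 30 v 15 does not deliver.
- Say that this figure does not apply to prolonged abstinence.
- Add the detectable difference for the primary end-point with its assumptions: 80% power, two-sided 5%, for about 10% v 52%, 20% v 66% or 30% v 75%. State that Fisher's test is used for planning only, so that it does not displace the generalized linear modeling already specified.
- Report the abstinence comparison as a difference in proportions with a 95% interval alongside that model, and state that a non-significant result will not be read as absence of effect.

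The cost is a few sentences and a less favourable stated power. No participants, visits or data are added.
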